11.12 Eosinophilic Esophagitis Symptom Score

Symptoms of Eosinophilic Esophagitis range from abdominal pain, gastroesophageal reflux, vomiting, and difficult swallowing. The symptoms will range from none to very severe as in Spergel⁵⁴. The symptoms will be in 3 categories and individual symptoms and total symptoms scores will be collected on a range of 0-4 (0-none, 1-mild, 2-moderate, 3-severe and 4-very severe).

Table 4: Eosinophilic Esophagitis Score

Symptoms	Score
Abdominal/Chest Pain	0-4
Vomiting/Regurgitation	0-4
Dysphagia	0-4
Total Score	0-12

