In addition, the change from baseline to end of treatment of the total symptom score and individual symptom scores (Abdominal/chest pain score, Vomiting score, and Dysphagia score) will be generated by treatment group and overall. The comparison of the change of individual symptom scores between the two treatment groups will be evaluated by using Fisher's exact tests.

The responses will be divided into three categories as suggested: Poor <30% improvement, good 30-70% improvement and excellent >70% improvement from baseline.

Percentage of subjects per response rate

The percentage of subjects showing an excellent response (≤ 1 eos/HPF), good response (2-14 eos/HPF), or poor response (≥ 15 eos/HPF) at the end of treatment will also be presented and analyzed between the two treatment groups using Fisher's exact test.

Eosinophilic Esophagitis Quality of Life Score

The Quality of Life score will also be reported for each treatment group at baseline and the end of treatment. The change from baseline to end of treatment will also be presented. The change in QOL scores between two treatment groups will be compared with two-sample t-test or Mann-Whitney test depending on the distribution of the change of the QOL score.

Combination Score:

Combination Score of four measures (Eosinophils/HPF, EREFS, investigator assessment and parental assessment of symptoms) will be calculated at baseline, end of treatment and end of study. The combination score will be calculated as (maximum eosinophils per high power field) + [10*esophageal endoscopy score (EREFs)] + [2* Parent assessment of esophageal symptoms (PEESS)] + [5*investigator assessment of EoE symptom activity]. The change from baseline to end of treatment will also be presented. The change in QOL scores between two treatment groups will be compared with two-sample t-test or Mann-Whitney test depending on the distribution of the change of the QOL score.

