#### **4.4.2.2 Eosinophilic esophagitis symptom and global assessment scores**

Summary statistics for individual eosinophilic esophagitis symptom score (Abdominal/Chest pain, Vomiting/Regurgitation, and Dysphagia) as well as investigator's eosinophilic esophagitis global assessment score at baseline, end of the double-blind treatment, and end of the open-label treatment as well as changes from baseline to end of the double-blind treatment and to end of the open-label treatment will be presented by treatment groups and overall (*Table 10*). The total EoE symptom score for each subject will be calculated and summary statistics at baseline, end of the double-blind treatment, and end of the open-label treatment, as well as the changes from baseline to end of the double-blind treatment and to end of the open-label treatment will be presented by treatment groups and overall. Improvement in symptom scores will be defined as a decrease in total eosinophilic esophagitis symptom score of two or more from baseline to end of the double-blind treatment and to end of the open-label treatment. Subjects will be categorized based on whether they improved their symptoms in two different ways. First, subjects who improved their symptom scores are considered as responders and subjects who did not improve their symptom scores are considered as non-responders. Second, subjects who improved their symptom scores will be categorized as poor improvement (<30%), good improvement (30-70%), and excellent improvement (>70%). RR or OR along with 95%

CI for the percentage of responders between two treatment groups will be presented. (*Table 11*).

In addition, frequency and severity EoE symptom scores measured by Pediatric Eosinophilic Esophagitis Symptoms Score (PEESS) will be examined. Summary statistics for the frequency and severity EoE symptom scores at baseline, end of the double-blind treatment, and end of the open-label treatment will be reported for each treatment group and overall. The changes in frequency and severity EoE symptom scores from baseline to end of the double-blind treatment and to end of the open-label treatment will be reported and Hodges-Lehmann estimates with 95% CIs for differences of medians of these changes between two treatment groups will be reported (*Table 12*).

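### SAP 4.4.2.2 grades symptom improvement as poor, good or excellent only for subjects who already improved by 2 or more points, so Table 11's poor row understates poor outcomes

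*SAP*

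**What the plan says.** The score has three symptom items, each rated 0 to 4, and Protocol 11.12, Table 4 gives "Total Score 0-12" for their sum.

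SAP 4.4.2.2 classifies subjects on this total in two ways. The first is binary: "Improvement in symptom scores will be defined as a decrease in total eosinophilic esophagitis symptom score of two or more from baseline", and "subjects who did not improve their symptom scores are considered as non-responders". The second grades by percentage: "subjects who improved their symptom scores will be categorized as poor improvement (<30%), good improvement (30-70%), and excellent improvement (>70". Table 11 gives the second classification three rows at Visit 10 and three at Visit 16. It has no row for anyone else and states no denominator. Its footnote says the three-way report is made at FDA's request.

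Protocol 13.6.4.2 has the same bands with a different subject: "The responses will be divided into three categories as suggested: Poor <30% improvement, good 30-70% improvement and excellent >70% improvement from baseline". It does not restrict them to subjects who improved.

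The Table 11 footnote on responders takes visit minus baseline and calls a subject a responder when that difference is 2 or more.

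**The concern.** A three-band scale whose lowest band is *poor* should show how many subjects did badly. Under the SAP sentence it cannot, because a subject must first have done reasonably well (a fall of at least 2 points) to be graded at all. A child whose symptoms return after milk is reintroduced is not *poor* in this table; that child has no grade.

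The design makes this relevant. Subjects are randomised after at least 6 milk-free weeks, and Visit 10 follows milk reintroduction. Protocol 8.2 names the return of symptoms in placebo subjects and non-responders as a risk of the trial. Worsening is thus an expected form of failure, and the grading has no place for it. At stake is one secondary table, but one the SAP says a regulator asked for.

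**Working it through.** The plan gives no power or target figure for this endpoint, so there is nothing to reproduce. The check is arithmetic on the definitions.

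**Inputs.** Total score: integer 0-12 (Protocol 11.12). Improvement: fall *d* of 2 or more (SAP 4.4.2.2). Percent improvement: *p* = *d*/*b*, with *b* the baseline total. Bands: <30%, 30-70%, >70% (both documents).

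**Step 1: when *poor* is possible.** The smallest graded fall is 2, so *poor* requires 2/*b* < 0.30, that is *b* > 6.67. At *b* = 6, 2/6 = 33.3% (good). At *b* = 7, 2/7 = 28.6% (poor).

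| Baseline | Falls graded *poor* under the SAP rule |
|---|---|
| 0-1 | subject can never be graded |
| 2-6 | none |
| 7-10 | exactly 2 (at 10, a fall of 3 is 30.0%, good) |
| 11-12 | 2 or 3 (3/11 = 27.3%, 3/12 = 25.0%) |

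There are 1 + 2 + ... + 11 = 66 baseline/fall pairs that get a grade: (4 × 1) + (2 × 2) = 8 poor, 30 good and 28 excellent. These count possible outcomes; they are not probabilities.

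**Step 2: who is left out.** There are 13 × 13 = 169 possible baseline/follow-up pairs. Of these, 78 are worse, 13 unchanged and 12 a one-point fall. So 78 + 13 + 12 = 103 get no grade, and 169 − 103 = 66 do.

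**Step 3: without the restriction.** Grading every subject with a baseline of 1 or more gives 12 × 13 = 156 pairs: 95 poor, 32 good, 29 excellent. *Poor* is then reachable from every baseline of 1 or more. Of the 103 ungraded pairs, 95 − 8 = 87 become poor. Three become good or excellent (2 to 1 is 50%, 3 to 2 is 33.3%, 1 to 0 is 100%). The other 13 have baseline 0, where the percentage is undefined.

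**Step 4: hypothetical illustration.** Take the 6 planned placebo subjects. Suppose one goes from 2 to 0 and five worsen from a baseline of at least 1. Out of 6, the SAP rule gives excellent 1/6 = 17%, good 0%, poor 0%, with five subjects in no row. Without the restriction it gives excellent 17%, good 0%, poor 5/6 = 83%. The excellent row is the same; only the *poor* row changes.

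**Step 5: footnote sign.** With change = visit minus baseline (the direction SAP 2.2.4 also uses), a decrease of 2 or more is a change of −2 or less. Table 11 asks for 2 or more. A subject going from 2 to 0 (change −2) is a responder by the text and a non-responder by the footnote; one going from 2 to 4 is the reverse.

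**The case against.** A reader might infer more than the documents support, in four ways.

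- *The arms are compared only among improvers, so randomisation is lost.* Not established. Protocol 13.6 sets the default denominator for percentages as the subjects in the population with data, and the SAP does not override it. Table 11 is specified for the ITT and PP populations. On that default, the good and excellent percentages fall as more subjects worsen, and the three rows add up to the responder percentage. The relative risk or odds ratio in SAP 4.4.2.2 is for responders, a whole-arm comparison. The Table 11 note promising a relative risk of improvement does not say that it covers the three grades.
- *Worsening subjects disappear from the analysis.* They are missing only from the three-grade rows. The same table counts them as non-responders and includes them in the change summaries, and Table 10 shows item changes from −4 to +4.
- *Poor is almost impossible.* Only the limit at baseline 6 is exact. The documents give no baseline distribution of the symptom score, so how often *poor* could occur is unknown. If improvement were read as any decrease, *poor* would be reachable from baseline 4 (17 of 78 pairs). But the SAP defines improvement as 2 or more points, and even the loose reading leaves unchanged and worsened subjects ungraded.
- *The protocol expressly grades everyone.* It does not. It speaks of responses, in a subsection that also defines responders, and it gives no rule for unchanged or worsened subjects or for a baseline of 0.

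These points stand and limit the consequence. They do not answer the central one: the SAP states a restriction that the protocol does not, and it leaves the *poor* row unable to report most poor outcomes.

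**Conclusion.** The point holds as a defect in one secondary classification. *Poor* is arithmetically excluded at baselines of 6 or less. Subjects who worsen, do not change or fall by 1 point have no grade. The *poor* row therefore understates poor outcomes, and the three rows need not sum to the arm total. The good and excellent percentages are not shown to be distorted if the protocol's default denominator applies.

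This rests on the SAP's own definition of improvement and on integer totals from 0 to 12. How many subjects are affected depends on baseline scores, which neither document gives. The primary analysis is untouched. It should be corrected, because Table 11 would otherwise report a different quantity from the one its labels suggest. The footnote sign is a separate plain error: programmed literally, it would label worsening subjects as responders.

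**What to change.** In SAP 4.4.2.2, delete the restriction to subjects who improved and grade every ITT subject with a score. Count <30% improvement, no change and worsening as *Poor (<30%)*, or put no change/worse in a row of its own.

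In Table 11:

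- Add separate rows for baseline 0 (percentage undefined) and for missing scores.
- State that the denominator is all ITT subjects in the arm (PP subjects in the PP repeat), so that the rows sum to the arm.
- Correct the responder footnote to a change, visit minus baseline, of −2 or less.

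One consequence should be accepted knowingly: a one-point fall from a baseline of 1, 2 or 3 will be graded good or excellent although the subject is a non-responder, because the two rules use different scales.

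The cost is one SAP sentence, a few table rows and a corrected footnote. No new data are needed, and the design and primary analysis do not change.

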#### **4.4.2.3 Percentage of subjects per response rate**

The percentage of subjects showing an excellent response ( $\leq 1$  eosinophils/HPF), good response (2-14 eosinophils/HPF), and poor response ( $\geq 15$  eosinophils/HPF) at the end of the double-blind treatment and at the end of the open-label treatment as well as RR (i.e., the percentage of subjects showing excellent response in the treatment group divided by the percentage of subjects showing excellent response in the placebo group) along with 95% CIs between two treatment groups will be presented (*Table 13*).

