6.2.2 Natural History of EoE

Unlike most IgE-mediated food allergies, patients with food induced EoE do not outgrow it. Less than 5% of our patients have outgrown their food allergy based on biopsy and symptom changes.⁷ Similar results have been seen in adult populations with no patients having outgrown EoE in 20 years of follow-up.⁵⁸ It is also known that a delay in diagnosis increases the risk of fibrosis and strictures.^{58,59} Therefore, a therapy that changes the natural history of EoE is needed.

As typical standard of care, an endoscopy is performed to confirm the diagnosis. Prior to the endoscopy, a patient is treated with a proton pump inhibitor to treat possible reflux, which can mimic symptoms of EoE. The first endoscopy includes biopsy of esophagus, stomach and duodenum to ensure that eosinophilic inflammation is isolated to the esophagus. A repeat

endoscopy is performed 2 months after any therapeutic measure (diet or medication changes).^{7,9} When a food is identified, the food is generally reintroduced about 2 years later followed by an upper endoscopy with biopsy as part of standard of care treatment at CHOP. However, at other institutions, foods are introduced as soon as 2 months after endoscopy.

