#### **2.4.2 Randomization and replacement**

Approximately 22 eligible subjects to obtain 18 completed subjects will be randomized in a 3:1 ratio into two different treatment groups, (1) to receive EPIT with Viaskin® Milk (500 µg of milk proteins) or (2) placebo (16 subjects in the active Viaskin® Milk group and 6 subjects in the placebo group). Subjects who are withdrawn after beginning the treatment phase of the study will not be replaced. However, sufficient subjects will be included to ensure the minimum sample size.

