#### **3.2 Sample size determination and power calculation**

The primary objective of this study is to determine whether mean maximum eosinophil counts is different in the subjects on the Viaskin Milk group compared to those on the placebo group. This is a pilot study in which we aim to identify efficacy of the Viaskin® Milk treatment. Sample size is based on projected subject volume. If efficacy is shown, our pilot data could be used to perform a power analysis for a larger study. We will recruit 38 subjects and plan to have 22 evaluable subjects with milk-induced EoE confirmed by endoscopy and biopsy. Approximately 20 subjects (15 subjects in the active Viaskin® Milk group and 5 subjects in the placebo group) will be randomized to two treatment groups to obtain 18 completed subjects assuming 10% dropout rate. This sample size will have 90% power to detect a difference of 40 in mean maximum eosinophil counts between the subjects receiving Viaskin® milk (mean maximum eosinophil count of 10) and the subjects on placebo (mean maximum

eosinophil count of 50) assuming a common standard deviation of 20 using a two group *t*-test with a two-sided significance level of 0.05.

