# Values will be expressed as n, n missing, mean  $\pm$  SD, median (IQR), and range. Hodges-Lehmann median differences between two treatment groups will be reported.

\* Improvement in total eosinophilic esophagitis symptom scores is defined as a decrease in total symptom scores of two or more from baseline to end of the double-blind treatment (visit 10) and from baseline to end of the open-label treatment (visit 16). If change in total symptom score (Visit 10 – baseline or Visit 16 - baseline) is 2 or greater than 2, subject is responder; if not, subject is non-responder. Values will be expressed as frequency counts (percentages).

\*\* Improvement will be reported as Poor, Good, and Excellent as FDA requested.

Relative risk with 95% CI of the improvement between two treatment groups will be presented.

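### At Visit 10 the planned relative risk for excellent (and good) histologic response will usually have a zero placebo denominator, and the SAP has no method for that case

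*SAP*

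**What the plan says.** SAP 4.4.2.3 sorts subjects into excellent (at most 1 eosinophil/HPF), good (2-14) and poor (15 or more) response, at the end of the double-blind period (Visit 10) and at the end of the open-label period (Visit 16). The between-group measure is a relative risk (RR) with a 95% CI. The section spells the ratio out for one category only: "the percentage of subjects showing excellent response in the treatment group divided by the percentage of subjects showing excellent response in the placebo group". Tables 13A (Visit 10) and 13B (Visit 16) each carry one RR column beside all three category rows. Neither the section nor the tables name a CI method, a zero-cell rule or a fallback measure.

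Protocol 13.6.4.2 has the same categories "presented and analyzed between the two treatment groups using" Fisher's exact test, which works with an empty cell. SAP 4.4.2.3 does not carry that test over.

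The placebo arm is small in either statement of its size. SAP 2.4.2 has "16 subjects in the active Viaskin® Milk group and 6 subjects in the placebo group"; SAP 3.2 has "15 subjects in the active Viaskin® Milk group and 5 subjects in the placebo group".

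**The concern.** A ratio with the placebo percentage underneath needs at least one placebo responder. Subjects qualify by showing 15 or more eosinophils/HPF on milk, and the sizing assumption has placebo averaging 50 after milk is reintroduced. With 5 or 6 such children, none at or below 1/HPF is the natural expectation. The cell of Table 13A that the SAP defines most explicitly would then be empty or infinite. What to put there (a continuity constant, an odds ratio, another measure) would be decided after the zero had been seen. That choice matters, because for the same data an ad hoc corrected interval can point to a different conclusion from an exact test.

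**Working it through.** **Inputs.** Placebo mean 50, active mean 10, common SD 20, two-sided 5% level (Protocol 13.2, SAP 3.2). Arms 16:6 (SAP 2.4.2) or 15:5 (SAP 3.2). Dropout 10% and 18 completers (SAP 3.2). Cut-offs from SAP 4.4.2.3. Neither document states an expected placebo response rate at Visit 10, so that rate is an assumption and a range is shown.

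**The plan's own figure.** Exact noncentral-t power for a difference of 40 with SD 20 is 91.1% for 18 completers split 14:4, close to the stated 90%. It is 95.5% for 15:5 and 97.8% for 16:6. The mean and SD are therefore being read as the plan uses them.

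**Placebo rates implied by Normal(50, 20), with a half-unit correction for counts.**
- Excellent: P(X < 1.5) = Φ((1.5 − 50)/20) = 0.0077.
- Below 15: P(X < 14.5) = Φ((14.5 − 50)/20) = 0.0379.
- Good: 0.0379 − 0.0077 = 0.030.
- Poor: 1 − 0.0379 = 0.962.

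A gamma or negative binomial distribution with the same mean and SD gives a still smaller excellent rate.

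**Chance of no placebo responder at Visit 10, (1 − p)^n, observed data.**

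| Assumed placebo rate p | n = 6 | n = 5 |
|---|---|---|
| 0.77% (excellent, Normal) | 95.5% | 96.2% |
| 3.0% (good, Normal) | 83% | 86% |
| 5% | 73.5% | 77.4% |
| 10% | 53.1% | 59.0% |
| 20% | 26.2% | 32.8% |

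The 5% row takes the ceiling of a natural-history statement in Protocol 6.2.2, "Less than 5% of our patients have outgrown their food allergy based on biopsy and symptom changes", as a rough proxy. The break-even rate, 1 − 0.5^(1/n), is 10.9% for n = 6 and 12.9% for n = 5.

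**Does a continuity correction rescue the RR?** Take the most extreme possible result, 16/16 v 0/6, and add 0.5 to each cell:
- RR = (16.5/17)/(0.5/7) = 13.6.
- SE of log RR = √(1/16.5 − 1/17 + 1/0.5 − 1/7) = 1.363.
- 95% CI = 13.6 × exp(±1.96 × 1.363) = 0.94 to 197.
- Fisher p = 1/C(22,6) = 1/74,613 = 0.00001.

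So with 0/6 on placebo this interval includes 1 whatever the active arm does.

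**LOCF.** SAP 3.3 imputes missing secondary endpoints by LOCF. A placebo dropout's last biopsy may be the milk-free screening one (0 to 10/HPF). Let q be the share of such values at or below 1 (not given; assumed). With 10% dropout the effective rate is 0.9p + 0.1q. For n = 6:
- p = 0.77%: zero in 70% (q = 0.5) or 51% (q = 1).
- p = 5%: zero in 55% (q = 0.5) or 39% (q = 1).

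**Where the RR should be estimable.** For 15 or more/HPF, the chance of a zero placebo count is 0.0379^6, about 3 in a billion. At Visit 16 all subjects have had active patches. If former placebo subjects reach the 33.5% excellent rate implied by Normal(10, 20), the denominator is zero in only 9% (n = 6) or 13% (n = 5).

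**The case against.** **The disease-threshold split is computable.** A reader might infer that the whole responder analysis fails. It does not. Response below 15/HPF is not a row of Table 13A, and its complement, 15 or more, is. If 10/16 active and 0/6 placebo subjects fell below 15, that row would be 6/16 v 6/6: RR 0.375, log-RR 95% CI 0.20 to 0.71. This stands, and it confines the point to the excellent and good rows.

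**A score interval for the RR exists.** The SAP names no CI method, and a score interval with a zero denominator has a finite lower limit and an infinite upper one. That is correct, so it would be too strong to say that no interval can exist. There is still no finite point estimate, and the SAP does not specify that interval.

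**The replacement would often be inconclusive too.** The sizing assumption implies about 34% excellent on active, roughly 5/16. For 5/16 v 0/6, Fisher p = 0.27 and the Newcombe risk difference is 0.31 (−0.11 to 0.56). True: six placebo subjects limit any method. The replacement does give a defined answer, and it separates the arms when the data do.

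**The placebo rate is inferred.** Also true. The Normal model is crude, and the natural-history figure does not describe a milk challenge of 1 week to 2 months. This is why the break-even rate is given. LOCF could lower the zero probability, in one scenario below half. But a denominator created that way would be an off-milk biopsy counted as tolerance of milk.

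**Other binary endpoints.** SAP Table 11 says "Relative risk with 95% CI of the improvement between two treatment groups will be presented", and SAP 4.4.2.7 plans RRs for categorical biomarkers. A reader might extend the point to these. The documents give no placebo rate for either, and eosinophil tails say nothing about symptoms or biomarkers, so no failure is shown there.

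**Consequence.** No decision rule rests on this RR. Counts by arm will be shown, and the protocol still names Fisher's test. This limits the harm to one secondary comparison.

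**Conclusion.** The concern holds for the Visit 10 excellent-response RR, the only RR that SAP 4.4.2.3 spells out, and for the good-response row of Table 13A. With 5-6 placebo subjects, the excellent-response denominator is zero in about 95-96% of trials under the plan's mean 50 and SD 20 with normality, and in 74-77% at an assumed 5% rate. It is zero more often than not for any rate below about 11% (n = 6) or 13% (n = 5). These figures take observed data and independent subjects, and LOCF may reduce them. Followed as written, the SAP would then usually yield no finite between-group estimate for this endpoint, and the obvious repair cannot exclude 1 even for perfect separation. The documents do not support a wider claim that histologic response cannot be compared at all, that Visit 16 fails, or that Table 11 and the biomarkers are affected. This should be changed before unblinding, as a repair to a secondary analysis; it does not touch the primary endpoint.

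**What to change.** In SAP 4.4.2.3 and Table 13A:

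- Make the risk difference the between-group measure, with a named 95% CI method (Newcombe, Miettinen-Nurminen or exact). For 16/16 v 0/6, Newcombe's interval is defined. The Wilson limits are 0.806 to 1 for active and 0 to 0.390 for placebo, so the lower limit is 1 − √((1 − 0.806)² + 0.390²) = 0.56 and the upper limit is 1.
- Restore the Fisher exact test of Protocol 13.6.4.2 for these categories.
- State the zero-cell rule: report the RR as a supplement only where the placebo count is non-zero.

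The cost is a few sentences and one table shell, with no new data. The downside is that the ratio-scale summary is lost or becomes secondary.
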